- a. Meals should be given at approximately the same time every day starting on Day -1 (time-matched to postdose meals) through Day 20. Breakfast will be given at ~1 hour postdose, lunch given at ~4 hours postdose, a snack given at ~8 hours postdose and dinner at ~12 hours postdose. All meals will follow the completion of all specified procedures at that timepoint.
- b. Panel A will be confined minimally from Day -2 through Day 21. Panel B will be confined within a week of starting their antipsychotic washout period through Day 21; minimally subjects will be confined from Day -6 through Day 21. Panel C will be confined minimally from Day -1 through Day 21.
- c. Single HR and BP measurements will be obtained at all postdose timepoints. On the following days, specific timepoints are noted:
- Day -1: Triplicate measurements time- matched to 8 hour post dose vital sign
 - Day 2 and Day 5: 8 hours post-dose (Panel A only)
 - Day 8, Day 11, Day 14 and Day 17: 8 hours post-dose
 - Day 10, Day 12, Day 13, Day 15, Day 16 and Day 18: 10 and 16 hours postdose
- d. Orthostatic assessments in HR and BP will follow semi recumbent vital sign assessments. Subjects should be standing for approximately 3 minutes prior to the orthostatic assessments. Orthostatic HR and BP measurements will be obtained on:
- Day -1: Time- matched to 8 hour post dose orthostatic vital sign.
 - Day 2 and Day 5: 8 hours post-dose (Panel A only).
 - Day 8, Day 11, Day 14 and Day 17: 8 hours post-dose
 - Day 10, Day 12, Day 13, Day 15, Day 16 and Day 18: 10 and 16 hours postdose
- e. For Panels A and B, single 12-lead safety ECG measurements will be at all postdose timepoints. On the following days, specific timepoints are noted:
- Day 1: Triplicate measurements within 2 hours prior to dosing.
 - Day 2 and Day 5: 8 hours post-dose (Panel A only).
 - Day 8, Day 11, Day 14 and Day 17: 8, 10 and 16 hours post-dose
- f. For Panels A and B, continuous (24-hour) Holter ECG measurements will be performed from approximately 30 minutes prior to dose administration and until 24 hours post-dose. ECG data will be extracted on:
- Day -1 (baseline measurement): time matched to dosing days at the following timepoints: 2, 6, 8, 10, 12, 16 and 24 hours
 - Day 7, Day 10, Day 13 and Day 16: predose, 2, 6, 8, 10, 12, 16 and 24 hours post-dose.
 - Day 18: 2, 6, 8, 10, 12, 16, 24, 36 and 48 hours post-dose.

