- a. Meals should be given at approximately the same time every day starting on Day -1 (time-matched to postdose meals) through Day 17. Breakfast will be given at ~1 hour postdose, lunch given at ~4 hours postdose, a snack given at ~8 hours postdose and dinner at ~12 hours postdose. All meals will follow the completion of all specified procedures at that timepoint.
- b. Participants will be confined minimally from Day -1 until Day 18 procedures are complete.
- c. Scheduled assessments are completed predose on dosing days and at any time on non-dosing days.
- d. Single HR and BP measurements will be obtained at all postdose timepoints. On the following days, specific timepoints are noted:
- Day -1: Triplicate measurements time- matched to 8, 10, 16 hours post dose vital sign
 - Day 1, Day 2, Day 5, Day 8, Day 11, Day 14: 8 hours post-dose
 - Day 3, Day 6, Day 7, Day 9, Day 10, Day 12, Day 13, Day 15 and Day 17: 8, 10 and 16 hours postdose
- e. Orthostatic assessments in HR and BP will follow semi-recumbent vital sign assessments. Subjects should be standing for approximately 3 minutes prior to the orthostatic assessments. Orthostatic HR and BP measurements will be obtained on:
- Day -1: Time- matched to 8, 10, 16 hours post dose orthostatic vital sign.
 - Day 1, Day 2, Day 5, Day 8, Day 11, Day 14: 8 hours post-dose
 - Day 3, Day 6, Day 7, Day 9, Day 10, Day 12, Day 13, Day 15 and Day 17: 8, 10 and 16 hours postdose
- f. Single 12-lead safety ECG measurements will be taken at all postdose timepoints. On the following days, specific timepoints are noted:
- Day 1: Triplicate measurements within 2 hours of dosing
 - Day 2, Day 5, Day 8, Day 11, and Day 14: 8, 10, 16 and 24 hours post-dose
- g. Continuous (24-hour) Holter ECG measurements will be performed from approximately 30 minutes prior to dose administration and until 24 hours post-dose. ECG data will be extracted on:
- Day -1 (baseline measurement): time matched to dosing days at the following timepoints: 2, 6, 8, 10, 12, 16 and 24 hours
 - Day 1, Day 4, Day 7, Day 10 and Day 13: predose, 2, 6, 8, 10, 12, 16 and 24 hours post-dose.
 - Day 15: 2, 6, 8, 10, 12, 16, 24, 36 and 48 hours post-dose.
 - If a subject discontinues study treatment at a dose of 16 mg or higher, an attempt should be made to collect 24-hour Holter data through 48 hours following their last dose.
- h. In the event the urine pregnancy test is positive or cannot be confirmed negative, a serum pregnancy test will be required.

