4 STUDY DESIGN

4.1 Overall Design

Specific procedures to be performed during the study, as well as their prescribed times and associated visit windows, are outlined in the SoA in Section 1.3. Details of each procedure are provided in Section 8.

This is a four-panel, randomized, placebo-controlled, parallel-group, multiple-dose, double-blinded, safety, tolerability, PK and QTc study of MK-8189 in participants with schizophrenia and healthy participants.

Panel A will enroll up to 16 healthy participants (8 Japanese and 8 non-Japanese) and Panel B will enroll up to 16 participants with schizophrenia or schizoaffective disorder to ensure at least 12 completers per group. Panel C will enroll up to 12 participants with schizophrenia/schizoaffective disorder and Panel D will enroll up to 20 participants with schizophrenia; participants may be replaced at the discretion of the Sponsor in consultation with the principal investigator. Participants will be randomized to MK-8189 or matched-placebo in a ratio of 3:1 (Panels A, B and C) and 3:2 (Panel D) according to a computer generated allocation schedule; within Panel A, 6 Japanese and 6 non-Japanese will be randomized to MK-8189 and 2 Japanese and 2 non-Japanese will be randomized to receive placebo according to the computer generated allocation schedule.

Participants with schizophrenia in Panel B and Panel D will be washed off their antipsychotic medication. The washout may start with a down titration of the antipsychotic treatment during the screening phase per direction of the investigator. Participants in Panel B and Panel D should not receive antipsychotics for at least 5 days or 3 half-lives (whichever is longer) prior to Day -1 Holter assessments. If deemed appropriate by the investigator, a participant may begin their washout as an outpatient, but should be confined within a week of starting the washout and minimally beginning on Day -6. In Panel C, participants with schizophrenia will remain on their study permitted atypical antipsychotic (AAP).

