If a participant does not tolerate escalation to the next dose, the participant may be titrated down to the previous dose (Panel A, B, C or D) or intermediate dose (Panel D). In addition, as discussed above, if the initial dosing cohort of Panel D or subsequent dosing cohort(s) does not tolerate the starting dose of 8 mg, subjects may be down-titrated to 4 mg. If appropriate medical care necessitates a down-dose, the investigator may do so independent of consultation with the Sponsor. If the participant tolerates continued dosing following down-titration, the participant may continue in the trial at that dose until study completion or may be re-challenged at a higher dose. Re-challenges are only to occur on regularly scheduled dose titration days, i.e. Day 4, Day 7, Day 10, etc. and will not extend the participant's time in the study. Participants will be followed for approximately 2 weeks after the last study treatment dose.

Panel A, healthy participants, will be confined to the clinical research unit (CRU) beginning on Day -2 through Day 21.

Participants with schizophrenia in Panel B and Panel D have a risk to experience exacerbations in psychotic symptoms both during the washout period as well as during the MK-8189 treatment period. To mitigate this risk, only participants with schizophrenia in the non-acute phase of their illness, with the onset of the first episode being no less than 2 years prior to study entry, will be recruited for study.

Panel B and Panel D, participants with schizophrenia, will be confined to the CRU within a week of beginning their antipsychotic medication washout and for at least the last 5 days of their washout (i.e. confinement will begin on Day -6 or earlier) and during the MK-8189 treatment to provide an enhanced level of participant supervision. If needed, rescue medication will be provided to treat withdrawal symptoms (see Section 6.5.1). Participants showing exacerbations in psychotic symptoms during the washout period will be re-evaluated for participation and referred for additional treatment as indicated.

Panel C, participants with schizophrenia, will be confined to the CRU beginning on Day -1 through Day 21.

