8.1.12 Domiciling

Participants in Panel A will report to the CRU on Day -2 prior to the scheduled day of study intervention administration on Day 1. Participants in Panel B and Panel D will be confined to the CRU within a week of beginning their antipsychotic washout and at least 6 days prior to treatment with MK-8189 on Day 1. Participants in Panel C will report to the CRU on Day -1 prior to the scheduled day of study intervention administration on Day 1. All participants in Panel A, Panel B and Panel C will remain in the CRU until Day 21 (72 hours following the last dose). Participants in Panel D will remain in the CRU until Day 18 (72 hours following the last dose). At the discretion of the investigator, participants may be requested to remain in the CRU longer.

Participants may be permitted to leave the unit, for emergency situations only, during the domiciling period at the discretion of the investigator after discussion with the Sponsor. The decision how to monitor the participant will be at the discretion of the investigator after discussion with the Sponsor.

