8.10.2 Treatment Period

Panel A: Healthy participants that meet selection criteria for enrollment will participate in Panel A, 16 participants in total. Participants will report to the CRU on Day -2 to undergo procedures in SoA.

Panel B and Panel D: Participants with schizophrenia that meet selection criteria for enrollment will participate in Panel B or Panel D, 16 participants or 20 participants, respectively, in total. Participants must be washed out from their antipsychotic medication for at least 5 days prior to the Day -1 Holter assessment. Participants will report to the CRU within a week of the start of their washout, minimally on Day -6.

Panel C: Participants with schizophrenia that meet selection criteria for enrollment will participate in Panel C, 12 participants in total. Participants will report to the CRU on Day -1 to undergo procedures in SoA.

On treatment days between Day 1 and Day 18 (Panel A, B and C) or Day 1 and Day 15 (Panel D), participants will be dosed once daily with MK-8189/placebo and have procedures

completed per the SoA. Participants will remain in the unit through Day 21 (Panel A, B, C) or Day 18 (Panel D) procedures and discharged at the discretion of the investigator.

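### The Day -2 pregnancy test scheduled in Panels B and D cannot meet inclusion 24's 24-hour window; separately, Panel D footnote b should read Day -6, not Day -1

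*Combined protocol and SAP*

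**What the plan says.** **Pregnancy testing.** Inclusion 24 in Section 5.1.2 makes a negative, highly sensitive test within 24 hours before the first dose mandatory for women of childbearing potential in Panels B, C and D. Section 8.3.5 sends the site to the SoA for test times. Appendix 2 (Section 10.2) sends it to Section 5.1 for the inclusion requirement, and allows further tests at the investigator's discretion or where local regulation requires them.

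The SoA has a serum test at screening and one urine test before dosing. Footnote m of the Panels A, B and C schedule puts the urine test on Day -2 for Panels A and B and on Day -1 for Panel C. The Panel D grid marks it on Day -2. Section 8.1.9.1 places dosing in the morning, and Section 8.11 allows 30 minutes either side.

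Exclusion 37 (Panels B, C and D) and exclusion 5 (Panel A) use a 48-hour window for the urine test. Panel A has no 24-hour criterion.

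**Confinement.** Footnote b of the Panel D SoA reads "Participants will be confined minimally from Day -1 until Day 18 procedures are complete". For Panels B and D, Section 4.1 says participants "should be confined within a week of starting the washout and minimally beginning on Day -6", and repeats Day -6 or earlier when it explains confinement. Section 8.1.12 has "at least 6 days prior to treatment with MK-8189 on Day 1" and Section 8.10.2 has "Participants will report to the CRU within a week of the start of their washout, minimally on Day -6". Panel B's own footnote b says "minimally subjects will be confined from Day -6 through Day 21".

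**The concern.** An eligibility criterion and the schedule meant to deliver it do not match. Section 8 calls for adherence to the SoA, and Section 5 allows no waiver of enrolment criteria. A site that treats the SoA as the full list of tests would reach Day 1 without the result that inclusion 24 demands. At stake is a pregnancy safeguard and a predictable eligibility deviation. No endpoint, estimate or analysis is affected.

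The footnote matters less. Section 4.1 confines Panels B and D through the end of washout and "during the MK-8189 treatment to provide an enhanced level of participant supervision", because psychotic symptoms may worsen. Read alone, footnote b would allow admission after that interval.

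**Working it through.** **1. Is the Day -2 reading sound?** For Panel B it rests on footnote m, which states the day in words. For Panel D it rests on the grid. In the same safety block, the baseline Holter and baseline vital signs sit in the Day -1 column, as footnotes g and d require, and the predose safety ECG sits in the Day 1 column, as footnote f requires. The pregnancy mark is one column before Day -1, so it is on Day -2. The administrative block of that table does look shifted by one column in places (dosing appears to start under Day -1), so it is not used for this step.

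**2. Age of the test at dosing.** The SoA columns run -2, -1, 1, so there is no Day 0. Let *t* be the clock hour of the test, *h* the nominal dosing hour and *T* the actual dosing hour, with *T* between *h* - 0.5 and *h* + 0.5.

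- Day -2 test: gap = 48 + *T* - *t*. Since *t* < 24, the gap always exceeds 24 + *T*, which is above 24 hours. All of Day -1 lies in between.
- Day -1 test: gap = 24 + *T* - *t*.

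The documents say only that dosing is in the morning. Taking *h* from 06:00 to 12:00 as an assumption:

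| Nominal dose | Day -2 test, any time (h) | Day -1 test, 14:00-20:00 (h) |
|---|---|---|
| 06:00 | 29.5 to 54.5 | 9.5 to 16.5 |
| 08:00 | 31.5 to 56.5 | 11.5 to 18.5 |
| 12:00 | 35.5 to 60.5 | 15.5 to 22.5 |

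For example, the overall minimum is 24 + 6 - 0.5 = 29.5 and the overall maximum is 48 + 12 + 0.5 = 60.5. The Day -2 test is therefore 5.5 to 36.5 hours past the limit.

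**3. Panel C.** A Day -1 test taken exactly at the nominal dosing hour, with the dose 30 minutes late, is 24.5 hours old and misses. It is safe only at or after *h* + 0.5.

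**4. The 48-hour window.** A Day -2 test is within 48 hours only if *t* is at or after *T*. Taken at *h* with the dose 30 minutes late, it is 48.5 hours old. A Day -2 test before the dosing clock time thus also falls outside the window in exclusion 37 and in Panel A's exclusion 5.

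**5. How many women.** Section 5 aims for approximately 40% women per panel: 0.40 x 20 = 8 in Panel D. At that target, 8 is a ceiling, because the number of childbearing potential is not given. No Panel B count is offered: Section 2.1 already reports tolerability in that panel, so it may be largely enrolled.

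**6. Confinement.** Day -6 to Day 1 is 6 days, which reproduces the lead time in Section 8.1.12. Day -1 to Day 1 is 1 day, so footnote b is 5 days short on paper. The Panel D grid itself supports Day -6. Its confinement row starts in the same column as the washout row, and the prerandomization drug screen, which footnote i ties to the day of admission, is marked at Day -6.

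**The case against.** The best defence of the plan is that inclusion 24 is itself an instruction to test within 24 hours. Appendix 2 points to it and permits extra tests, a physician must review every criterion (Section 8.1.2), and the SoA asks for clinical status to be rechecked before the first dose. Other safeguards remain: serum testing at screening, the Day -2 urine test with serum confirmation if it is not clearly negative, low-user-dependency contraception or abstinence, and review for early undetected pregnancy. On this view the gap is only one of test recency.

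Much of that stands, and it limits the consequence. It does not close the gap: the extra test in Appendix 2 is discretionary, Section 8.3.5 directs the site to the SoA for timing, and the SoA contains no test that can satisfy a mandatory criterion in Panels B and D.

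On footnote b the defence largely succeeds. It sets a minimum, so admission on Day -6 does not breach it, and the body text and the grid both require or show Day -6.

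**Conclusion.** The scheduling mismatch is real and does not depend on the assumed dosing hour: no time on Day -2 is within 24 hours of a Day 1 dose. The 29.5 to 60.5 hour range does rest on the 06:00 to 12:00 assumption. Panels B and D cannot comply from the SoA alone; Panel C can, if the Day -1 test is late enough; Panel A is touched only through its 48-hour window.

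Three stronger readings should be resisted.

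- A reader might infer that following the protocol leads to ineligible women being dosed. It does not, because inclusion 24 binds the site as much as the SoA does. The fault is that compliance needs an unscheduled test.
- A reader might infer that inclusion 24 and exclusion 37 contradict each other. They do not. Read in parallel with exclusion 5, exclusion 37 acts on a positive result, and both criteria can apply together.
- A reader might infer that Panel D participants would go through washout unsupervised. The confinement row, the admission drug screen and Sections 4.1, 8.1.12 and 8.10.2 all point to about Day -6, so footnote b is an error of wording.

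**What to change.** **Pregnancy test**

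- *Panel D:* in the SoA, schedule the urine test on Day 1 predose, with the result in hand before dosing, or on Day -1 in the afternoon or evening (for example 14:00 to 20:00).
- *Panel B:* separate the pregnancy row from footnote m, which it shares with Panel A and with many other assessments, and make the same change.
- *Panel C:* give the Day -1 test the same time limit.
- *Optional, Panels B and D:* keep the Day -2 test as well. Randomization may occur on Day -1, so a later test alone could find a pregnancy after allocation. This matters most for Panel B, where Section 5.5 provides no replacement; Panels C and D allow it.
- *Panel A:* require the Day -2 test at or after the planned dosing clock time plus 30 minutes.
- Leave the 48-hour windows in exclusions 5 and 37 as they are.

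**Footnote b.** Give Panel D the Panel B rule: confined within a week of starting washout, minimally from Day -6, until Day 18 procedures are complete.

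**Cost.** A few SoA edits and no added visit, since participants are already in the unit. There is no extra test if the Day -2 test is moved, and one per woman of childbearing potential if it is also kept. A woman found pregnant after allocation but before dosing uses one allocation number and would not enter the safety population, which requires at least one dose (Section 9.5).

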2 INTRODUCTION

2.1 Study Rationale

This study will evaluate safety, tolerability and pharmacokinetics (PK) of multiple oral doses of MK-8189, an inhibitor of phosphodiesterase 10A (PDE10A), in healthy participants and participants with schizophrenia at doses that are higher than those explored in the previous multiple-ascending dose study (MK-8189 PN003-06). Initially this protocol was intended to evaluate doses up to and including doses of 24 mg. However, doses up to 24 mg have been generally well tolerated in Panel A and B, and thus this amendment will allow the safety and tolerability assessment of doses up to and including 48 mg. This study will also evaluate the effect of MK-8189 on QTc.

The clinical dose of MK-8189 is currently unknown; however, 12 mg has demonstrated antipsychotic activity in acute exacerbation of schizophrenia and was generally well tolerated. Based on data from the current protocol as well as the potential for increased efficacy at higher doses of MK-8189, doses of MK-8189 as high as 24 mg are being considered for evaluation in Phase 2. Therefore, the current study, which will evaluate doses up to 48 mg of MK-8189 as monotherapy and up to 24 mg of MK-8189 as add-on therapy, would support safety and tolerability margins for doses as high as 24 mg or 16 mg, when given as monotherapy or as adjunct therapy, respectively. Therefore, these data would potentially support dosing in the presence of intrinsic and extrinsic factors which may increase MK-8189 exposure (e.g. CYP3A inhibition). In addition, if titration to supratherapeutic doses is achievable, this trial could support robust characterization of the effect of MK-8189 on QTc, which would depend on determination of the final clinical dose. Inclusion of healthy Japanese subjects will support the global clinical development in Japan.

It is recognized that an undesirable property of some non-antiarrhythmic drugs is their ability to delay cardiac repolarization leading to increased risk of development of life-threatening cardiac arrhythmias such as Torsade de Pointes (TdP) and possibly other ventricular tachyarrhythmias. The potential effect of a drug on cardiac repolarization can be measured as prolongation of the QT interval on ECG recordings. There is in general a qualitative relationship between substantial QT prolongation and the risk of TdP. The current trial will evaluate in a rigorous manner the impact of administration of MK-8189 on the QTc interval, to determine the risk of cardiac repolarization prolongation. While MK-8189 data to date do not suggest a QT prolongation risk, in fact, many antipsychotics are known to prolong QT. As MK-8189 is expected to be used as adjunct therapy, the QTc effect of MK-8189 will be an important assessment in the present study.

2.2 Background

Refer to the Investigator's Brochure (IB)/approved labeling for detailed background information on MK-8189.

[figure not shown]
2.2.1 Pharmaceutical and Therapeutic Background

[figure not shown]
MK-8189 is a potent and selective inhibitor of PDE10A that is being developed as a novel therapeutic for the treatment of schizophrenia. The PDE10A enzyme metabolically inactivates the ubiquitous second messengers, cyclic adenosine monophosphate (cAMP) and cyclic guanosine monophosphate (cGMP) [Bender, A. T. and Beavo, J. A. 2006] and is highly expressed in the target nucleus of the corticostriatal pathway, the striatum [Seeger, T. F., et al 2003]. Preclinical pharmacology studies demonstrate that PDE10A inhibition increases cAMP/cGMP signaling in pathways that have been associated with underlying pathology (glutamate) as well as clinically validated therapeutics (dopamine D2 receptor antagonists) for schizophrenia. Enhanced signaling in these pathways is hypothesized to restore behavioral inhibition that is impaired in schizophrenia [Grauer, S. M., et al 2009] [Schmidt, C. J., et al 2008]. PDE10A inhibitors may potentially be an alternative treatment as monotherapy and/or adjunct treatment in schizophrenia patients who have inadequate response to first line atypical antipsychotic (AAP) treatment.

[figure not shown]
